9.2. Eligibility criteria

9.2.1. Inclusion criteria

- (a) District Health Officer or District TB Supervisor (or other DHO-appointed TB focal person) from the Phase 1 Southwestern Uganda region which includes 2 intervention and 2 control DHO groups (of 5-10 DHOs/group)
- (b) By definition, the DHO and District TB Supervisors in Uganda are all ≥ 18 years of age

9.2.2. Exclusion criteria

- (a) Planned departure from position as DHO or TB District Supervisor prior to enrollment.

9.3. Enhanced Business Training

Building on business training introduced within the SPIRIT intervention, we will provide additional management training (using a technique referred to as “Gap Analysis”⁴⁸) to a subset of SPIRIT intervention DHO groups, in the southwestern Uganda region, in order to evaluate the impact of enhanced business training on ongoing IPT initiation at quarterly meetings.

9.4. “Training-of-trainers” curriculum intervention

The “Training-of-trainers” (ToT) curriculum will include materials to support business training including slides and information materials that cover leadership and management skills taught to SPIRIT intervention-group DHOs over the first 3 years (Phase 1) of teaching mini-collaboratives. The ToT program will be designed such that intervention DHOs will provide business management and leadership training quarterly to their respective District Health Teams (DHT).

9.4 Measures

9.4.1. Measures to evaluate the effect of enhanced business training will include changes in IPT initiation (as measured in Phase 1: see section 5.6.1), change in self-assessed leadership and management skills as measured by the modified LDBQ (see section: 7.2) and qualitative interviews (see section 7.2), as well as measures of attendance during enhanced business training sessions among intervention group DHOs.

9.4.2. Measures of implementation of the ToT intervention will include DHO fidelity to the training curriculum materials when DHOs provide quarterly business training to their respective DHTs, as measured by participation observation during meetings by our study staff and time spent on training at quarterly meetings.

9.5. Outcomes

The outcomes for this study aim will include changes in IPT initiation rates in Phase 2 intervention vs. control districts (see section 5.6.), and fidelity to implementation of the ToT program as defined by completion of trainings covering the full ToT curriculum.

9.6. Data Management & Statistical Considerations

9.6.1. Data Collection & Management

Staff will record all attendance at meetings on paper lab logs, or password-protected study computers. Data from these logs or devices will be entered and transferred via a secure electronic transfer to our data center facility in Kampala and stored on a secure server.

9.6.2. Analysis

The statistical analyses of IPT uptake will use the same methods as described for Phase 1 (see Section 5.7), limited to the SPIRIT trial intervention and control districts from the Southwestern region of Uganda. However, the outcome will be evaluated by district, rather than the pair-matched DHO groups evaluated in Phase 1.

10. “Training-of-trainers” curriculum impact on district-level management and health outcomes

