1.1 Study Synopsis

We will evaluate the effect of the SPIRIT intervention on provider prescription and patient use of a 6-month course of IPT among all adults in HIV care in Uganda. SPIRIT is a multicomponent intervention based on the PRECEDE model of behavioral change targeted primarily at the level of the DHO. The SPIRIT intervention deploys predisposing (teaching collaborative); enabling (SMS); and reinforcing (reporting collaborative) components. The study design is a cluster randomized trial where the unit of randomization is a group of 4-6 DHOs: seven groups randomized to the intervention and seven to the current country standard of care. The primary endpoint of the study is the rate at which eligible HIV-positive adults (defined by the Ugandan Ministry of Health) receive a prescription for INH in health facilities overseen by DHOs participating in the SPIRIT trial. Secondary endpoints include: a) IPT completion measured through analyzing successful INH refill patient-visits; b) DHO and health worker attitudes towards IPT; c) TB incidence; d) DHO leadership and management skills and e) costing and cost-effectiveness. The overall goal of the proposal is to test the effectiveness of a scalable approach to increasing IPT uptake through a behavioral change model targeting DHOs (middle managers) within the Uganda health infrastructure. In a second phase of the trial (Phase 2: Years 4-5), we will: a) evaluate the impact of enhanced business management training, focused on SPIRIT intervention DHOs in

the Southwestern Uganda region, on IPT initiation in the region during Phase 2; and b) implement a training of trainers (ToT) curriculum among DHOs enrolled in the SPIRIT trial from the southwestern region of Uganda to determine if DHO-provided business management training of their District Health Team (DHT) members can improve the management skills of the DHT members. **Figure 1** provides a schematic overview of the SPIRIT study:

Figure 1. SPIRIT study schema. For illustration we show 10 DHO groups per arm with 5 DHOs per group. The trial will enroll 14 DHO Groups: 7 intervention and 7 control. In Years 4 and 5 (Phase 2), the trial will be limited to the 14 districts in the Southwestern region of Uganda.

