5.2 Randomization

The SPIRIT trial investigators will form up to 14 groups of 4-7 DHOs (Figure 1). When possible, groups will be formed based on geographic, socio-demographic, and health systems characteristics. The groups will be pair-matched on geographical, socio-demographic and health systems characteristics to improve statistical efficiency. For both the creation of the groups and construction of matched pairs, geographic proximity will be optimized to facilitate DHO mini-collaboratives in the SPIRIT intervention and minimize contamination between arms. Randomization will be performed using a random number generator in standard statistical software, and overseen by the study statistician. One group in each of the 7 matched pairs will be randomized to the intervention, and one to the control condition.

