10.5 Analysis

For analysis of our primary outcome of interest among DHT members in Phase 2, we will compare changes in self-reported proficiency in business and leadership skills from Phase 2 baseline to Year 5 of follow-up, as measured by LDBQ survey responses, among DHT members in intervention vs. control districts using the same methods as for Phase 1 (see Section 5.7). We will also compare secondary outcome measures, including district-level health metrics and the number of quality improvement initiatives, from Phase 2 baseline to Year 5, in intervention vs. control districts. Qualitative data analyses will employ qualitative assessment methods as described for Phase 1 above (Section 5.6.2).

11. Human Subjects

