Statistical inference: Recall that 4-7 districts were put into groups for the purposes of pair-matching and treatment randomization. In the intervention arm, these clusters are the basis for mini-collaborative activities. In the control arm, there are **no** mini-collaborative meetings or any other study activities. Instead, the control condition corresponds with the standard of care. Therefore, it is reasonable to assume districts in the control arm are independent.

Given this independence structure (at the mini-collaborative level in the intervention arm and at the district level in the control arm), we take the following approach to statistical inference. In the primary analysis, we will assume there are 7 independent units corresponding to the mini-collaboratives in the intervention arm, and 40 independent units corresponding to the districts in the control arm (total $N = 47$). In sensitivity analyses, we will treat the randomized cluster as the independent unit (total $N = 14$). In all analyses, we will use the influence function for standard error estimation [11] and the Student's t -distribution with $(N - 2)$ degrees of freedom as finite sample approximation to the standard normal distribution [11].

Primary analyses will break the matched pairs used for randomization. For completeness, we will also conduct a paired t-test ($N = 7/\text{arm}$), implement a permutation test, and also estimate the intervention effect with mixed (random) effects models and with generalized estimating equations (GEE) [13, 14].

Sensitivity analyses: In addition to the sensitivity analyses described above, we will conduct the following sensitivity analyses. To minimize the impact of secular trends, we will exclude the “100-day IPT push” (Q3-2019). To better understand the impact the COVID-19 pandemic which caused a lockdown to be initiated in Q2-2020, we will conduct an analysis excluding the post-lockdown period and an analysis excluding the pre-lockdown period. Given the expected skewed distribution of clinic sizes, we will conduct two sensitivity analyses excluding clinics with baseline active care size exceeding 2500 patients and exceeding 5000 patients.

Subgroup analyses: We will repeat the above analyses within strata defined by sex, baseline active care size (≤ 1000 vs. >1000), and region.

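### Phase 2 IPT uptake is evaluated by district although DHO groups were randomised, with only 2 groups per arm in the Southwest and no statement that group clustering is kept

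*Protocol*

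**What the plan says.** - **Randomised unit.** Protocol 1.1 states that "the unit of randomization is a group of 4-6 DHOs". Protocol 5.2 adds: "One group in each of the 7 matched pairs will be randomized to the intervention, and one to the control condition". Protocol 4 says the pairs were formed within region.
- **Phase 2 scope.** The Figure 1 legend in Protocol 1.1 says "the trial will be limited to the 14 districts in the Southwestern region of Uganda". Protocol 9.2.1 describes the region as having "2 intervention and 2 control DHO groups (of 5-10 DHOs/group".
- **Phase 2 IPT uptake (Aim 5).** Protocol 9.6.2 points to the methods of 5.7, with one change: "the outcome will be evaluated by district, rather than the pair-matched DHO groups evaluated in Phase 1".
- **Phase 2 DHT outcomes (Aim 6).** Protocol 10.5 compares change in survey scores "among DHT members in intervention vs. control districts using the same methods as for Phase 1", citing 5.7. It does not name the independent unit.
- **Dependence.** SAP section 2, under statistical inference, says: "In the intervention arm, these clusters are the basis for mini-collaborative activities". For Phase 1 it therefore counts each intervention mini-collaborative as one independent unit, but takes control districts as independent of each other.
- **What is absent.** The SAP covers Phase 1 health outcomes only. Neither document gives a Phase 2 ICC, power figure or number of independent units.

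**The concern.** Districts entered the trial in groups. Protocol 5.2 forms those groups on geography and shared characteristics where possible. Intervention DHOs in a group then share a coach and meetings for three years, and the theory of the intervention is that attitudes spread within the group. Phase 2 adds further training to the same intervention groups. Positive correlation between districts of one group is therefore to be expected, at least in the intervention arm.

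The wording of 9.6.2 puts the district in place of the group. Where the protocol means to keep group clustering it says so: 6.5.2.1 states that the IPT completion analysis accounts for randomisation group and for DHO within group. Section 9.6.2 has no such sentence. If the district becomes the independent unit, the Aim 5 comparison has a standard error that is too small and far too many degrees of freedom. Its p-values and intervals would then claim more than 4 randomised groups support.

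**Working it through.** **1. The plan's own power figure.** Phase 2 has none. The nearest is SAP 6.3: 7 groups per arm, 22 vs 32 per 100 person-years, k = 0.25, about 21,500 person-years per group, one-sided 5%, 80% power. The usual cluster formula for rates is

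c = 1 + (z_α + z_β)² × [(λ0 + λ1)/y + k²(λ0² + λ1²)] / (λ0 − λ1)².

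- Bracket: 0.54/21,500 + 0.0625 × (0.0484 + 0.1024) = 0.00945.
- c = 1 + (1.645 + 0.842)² × 0.00945/0.01 = 6.84, so 7 per arm, with power 80.9%.

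The figure reproduces, with the randomised group as the unit.

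**2. Group-level randomisation test in the Southwest.** Protocol 5.7, which Phase 2 inherits, is two-sided.

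- Pairs kept: 2² = 4 allocations, smallest two-sided p = 2/4 = 0.50.
- Pairs broken: C(4,2) = 6 allocations, smallest two-sided p = 2/6 = 0.33.

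Neither can reach 0.05.

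**3. Group-level t-test.** Two-sided 5% critical values are 12.71 on 1 df (pairs kept) and 4.30 on 2 df (pairs broken). The value for 14 independent districts is 2.18 on 12 df. In null simulations the group-level tests hold their size (0.049 to 0.050). At the SAP planning inputs with 2 groups per arm, simulated two-sided power is about 15% unpaired and 9% paired, the latter assuming no gain from matching.

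**4. District-level test with no true effect.** Normal outcomes were simulated for 14 districts in groups of 4 and 3 per arm, with a pooled t-test on 12 df at two-sided 5%. The ICC is not in the documents and was varied as an assumption.

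| Within-group ICC | Rejection, ICC in both arms | 95% interval coverage, both arms | Rejection, ICC in intervention arm only |
|---|---|---|---|
| 0 | 5.0% | 95.0% | 5.0% |
| 0.05 | about 6.5% | about 93.5% | about 6% |
| 0.10 | about 8% | about 92% | about 6.5% |
| 0.20 | about 12% | about 88% | about 8% |
| 0.30 | about 16% | about 84% | about 10% |
| 0.50 | about 24% | about 76% | about 14% |

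With groups of 4 and 3, the variance of an arm mean is inflated by 1 + [(16 + 9)/7 − 1] × ICC = 1 + 2.57 × ICC. That is 1.26 at ICC 0.10 and 1.77 at 0.30.

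**5. Carrying over the SAP's Phase 1 structure.** With 2 intervention groups and 7 control districts on 2 + 7 − 2 = 7 df, rejection is 6.8% at ICC 0, 9.0% at 0.10 and 13.0% at 0.30 (ICC in both arms). This does not restore 5% either.

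**6. Unit counts.** 14 districts in 4 groups is 14/4 = 3.5 per group.

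- 4–6 per group (Protocol 1.1) implies 16–24.
- 4–7 per group (Protocol 5.2; SAP section 1) implies 16–28.
- 5–10 per group (Protocol 9.2.1) implies 20–40.

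None contains 14. The count matters: at ICC 0.10 in both arms, 5 or 10 districts per group would give 9.9% or 15.9% rejection.

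**The case against.** **Section 9.6.2 need not mean independence.** Measuring an outcome by district is different from taking the district as the independent unit. The SAP separates the two in Phase 1, and the inherited text in 5.7 refers to the matched design and to the limited number of independent units. This stands as a possible reading. But the sentence sets the district against the pair-matched group and keeps nothing of the group, so a reader cannot tell which variance is meant.

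**The SAP accepts dependence only in the intervention arm.** Correct, and the last column of the table follows that assumption. The excess over 5% is then roughly half or less, but it remains.

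**The ICC is assumed and a t-test stands in for TMLE.** Both are true. Baseline adjustment could reduce residual correlation, and at ICC 0 there is no problem.

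**A Phase 2 plan may exist elsewhere.** The SAP says that plans for business outcomes are available separately. That may cover Aim 6, but 9.6.2 as written still governs Aim 5 in these documents.

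Three stronger readings are tempting and are not supported:

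- A reader might infer that no group-level test can reach 5%. That holds for randomisation tests only; a t-test on 1 or 2 df can reach it, relying on normality and with little power.
- A reader might infer that Aim 6 is also switched to districts. The switch in 9.6.2 covers IPT uptake only. In 10.5 the districts identify the arms, and the defect there is silence on the unit.
- A reader might take 20–40 districts from 9.2.1. That criterion admits DHOs or TB supervisors, so the range may count people: two per district gives 28, or 7 per group.

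**Conclusion.** The point holds for Aim 5 as an unsafe and incomplete specification. As worded, 9.6.2 replaces the randomised group by the district and does not keep group clustering, against the SAP's own view of the intervention arm. If districts are then treated as independent, a nominal 5% test runs at about 8% to 24% for ICC 0.1 to 0.5 in both arms, or about 6.5% to 14% with correlation in the intervention arm only, and intervals are too narrow. These sizes rest on an assumed ICC, normal outcomes, 14 districts and an unadjusted test. The direction needs only a positive ICC.

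For Aim 6 the conclusion is narrower: the independent unit is not named. The mismatch in district and group counts is secondary and needs reconciling. The Phase 1 primary analysis is not affected.

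**What to change.** - **Protocol 9.6.2:** keep the district as the level at which IPT uptake is measured. State that Phase 2 standard errors and degrees of freedom come from the 4 randomised groups, and say whether the pairs are kept (1 df) or broken (2 df).
- **Protocol 10.5:** state the same independent unit for the DHT outcomes.
- **Reporting:** present Phase 2 mainly as estimates with group-level intervals, and show district-level results beside them as descriptive. Whether to rule out any significance statement is a matter of judgement; the estimates should carry the message.
- **Counts:** reconcile the 14 Phase 2 districts with the group sizes in 1.1, 5.2, 9.2.1 and the SAP. Say whether each range counts districts or people, and whether districts created by the 2019 divisions are included.

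The change is to wording only and needs no new data. The price is wide intervals: against 12 df, the t multiplier alone rises by 4.30/2.18 = 1.97 with pairs broken or 12.71/2.18 = 5.83 with pairs kept.

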10.1 Objective

Objective: To determine if having DHOs provide business leadership and management training to their District Health Teams (DHTs) can improve district-level management practices and health outcomes.

10.2 Recruitment & Enrollment of District Health Team (DHT) members

10.2.1 Recruitment

The SPIRIT Project Coordinator and study research assistants will work with the DHOs participating in the SPIRIT trial from the Southwestern Uganda region to obtain contact information for their DHT members. SPIRIT study staff will initiate contact with the DHT members by email, phone or in-person, to recruit for participation Phase 2 of the SPIRIT study.

10.2.2 Consent Process

Upon contacting the DHT members, the SPIRIT Project Coordinator or study research assistants will describe the business training planned for Phase 2 and the objectives of the study, and screen for enrollment. All eligible DHT members that agree to participate will provide written consent. If a DHT members departs from his/her position, we will consent the incumbent DHT member for study participation.

10.2.3 Screening for Enrollment

Study staff will screen all DHOs and/or District TB Supervisors reached during recruitment (10.2.1 above) for the eligibility criteria noted below.

10.2.3.1 Inclusion Criteria

- (a) District Health Team (DHT) member in Uganda from the Phase 1 Southwestern Uganda region districts
- (b) By definition, the DHT members in Uganda are all ≥ 18 years of age

10.2.3.2. Exclusion criteria

- (a) Planned departure from position as DHT Member prior to enrollment.

10.3 Outcome Measures

10.3.1 Leadership and Management Measures

We will use a mixed methods approach to evaluate self-perceived business leadership and management skills among DHT members in intervention and control districts that includes longitudinal self-assessment surveys with the modified LDBQ survey and focus group discussions (among intervention DHT members), key informant interviews (among control DHT members) guided by components of the World Management Survey, as described above (see Section 7.2). We will also conduct evaluation of implementation processes such as DHT attendance at DHO-led business training meetings and the number and content of health care quality improvement initiatives/actions taken by DHT members during Phase 2.

10.3.2 District Level Health Measures

We will obtain publicly available health outcomes as measured by the Uganda Ministry of Health at the district level from all Phase 2 districts in Southwestern Uganda. Health outcomes will include the metrics shown in **Table 3**, supplemented by other District-level health outcomes measured by the Ministry of Health and selected by DHOs or study investigators.

Table 3: District-level health measures

District Health Team Member	District-Level Health Metrics
Assistant District Health Officer: Maternal and Child Health	1 st antenatal care (ANC) visit attendance during 1 st trimester
Cold chain technician	DPT3 Immunizations
District TB/Leprosy supervisor	TB treatment completion or TB cure
Malaria Focal Person	Pregnant patients receiving intermittent preventive therapy for malaria (IPTp)
HIV focal person	ART Quarterly report: Missed visits (proportion of scheduled visits missed among patients living with HIV active in care)
Health Facility In-Charges	Out-patient Department (OPD) new patient attendance

10.4. Data Collection

Annual leadership and management surveys will be conducted at Phase 2 baseline (trial year 3) and years 4 and 5 of follow-up. Focus group discussions and key informant interviews will be audio recorded and translations will be data entered into appropriate software on password-protected study computers. Data from interviews will be transferred via a secure electronic transfer to our data center facility in Kampala and stored on a secure server. District level health metrics (**Table 3**), all of which is de-identified (aggregate data at the District level) will be obtained by study staff in collaboration with the Ministry of Health via electronic data queries from the Ugandan District Health Information System (DHIS2).

10.5 Analysis

For analysis of our primary outcome of interest among DHT members in Phase 2, we will compare changes in self-reported proficiency in business and leadership skills from Phase 2 baseline to Year 5 of follow-up, as measured by LDBQ survey responses, among DHT members in intervention vs. control districts using the same methods as for Phase 1 (see Section 5.7). We will also compare secondary outcome measures, including district-level health metrics and the number of quality improvement initiatives, from Phase 2 baseline to Year 5, in intervention vs. control districts. Qualitative data analyses will employ qualitative assessment methods as described for Phase 1 above (Section 5.6.2).

11. Human Subjects

11.1 Risks to Human Subjects

Potential Risks to Human Subjects

There are relatively few risks to study participants, as the proposed research intervention aims to improve implementation of recommended Uganda Ministry of Health IPT guidelines. There are no “experimental” drugs in this study. We will be measuring the uptake of standard and approved drugs-- isoniazid and B6 that will be provided through the Uganda health system. The primary risks involved in study participation are inadvertent disclosure of HIV or suspected TB status by study staff with associated stigma (Aim 2).

11.2 Adequacy of Protection against risks

11.2.1 Informed Consent

Trained research staff will obtain informed consent, as follows:

1. Aim 1 – Cluster randomized trial: Written informed consent will be obtained from DHOs and their TB District Supervisors or other DHO-appointed TB focal person, for participation in the SPIRIT Aim 1 cluster randomized trial, including behavioral surveys.

2. Aim 1 – Behavioral surveys: Written informed consent will be obtained from frontline clinic providers participating in behavioral surveys.

3. Aim 4&5 – ‘Training-of-trainers’ curriculum: Written informed consent will be obtained from District Health Team members.

All consent forms will be translated into the local language and back translated into English to ensure correct use of language. Consent forms will be read aloud to participants by trained staff. The informed consent will describe the purpose of the study, all the procedures involved, and the risks and benefits of participation. Interviewers will ask participants to summarize the study and explain the reasons why they want to participate. Either a signature or a thumbprint (for those who cannot read) will be acceptable to confirm informed consent for participation in the study, in the case of written consent forms.

